3.1 RANDOMIZATION

Subjects will be randomized to receive either low or high dose of RO7239361 or placebo according to a computer-generated randomization scheme.

During the screening visit, the investigative site will enter into the enrollment option of the Interactive Web Response System (IWRS) designated by Roche for assignment of a

subject number that will be unique across all sites. Once it is determined that the subject meets the eligibility criteria following the screening visit, the investigative site will enter into the IWRS to randomize the subject to one of the double-blind treatment groups.

Eligible subjects will be randomized in a 1:1:1 ratio to high dose RO7239361 (35/50 mg), low dose RO7239361 (7.5/15 mg), or placebo. The randomization will be stratified by:

- Age (6 through 7 vs 8 through 11)
- CS regimen: daily (prednisone, prednisolone or deflazacort) vs intermittent (any non-daily dosing of prednisone, prednisolone or deflazacort).

After 48 weeks on double-blind treatment, subjects continuing on study treatment will enter the open-label period. Placebo subjects will be re-randomized through IWRS and assigned to one of the RO7239361 dose groups.

3.2 DATA MONITORING

There will be an independent data monitoring committee (iDMC) for this study. The iDMC charter will document the iDMC scope, frequency of review, and membership.

The iDMC shall have access to partially unblinded data (coded treatment assignments) including but not limited to the following: the frequency and spectrum of serious adverse events (SAEs); Grades 3 to 4 laboratory abnormalities; occurrence of malignancies, if any; and other select AEs of interest. The iDMC shall act as an advisor to the Sponsor and have responsibility for safeguarding the subjects' interests, and will make recommendations to the Sponsor on the conduct of the study.

4. STATISTICAL METHODS

4.1 ANALYSIS POPULATIONS

The analyses will use several populations as defined below.

4.1.1 Enrolled Population

The Enrolled Subjects Population includes all subjects who sign an informed consent form.

4.1.2 Randomized Population

The Randomized Subjects / Intention to Treat (ITT) Population includes all enrolled subjects who receive a randomization treatment assignment.

4.1.3 Modified Intent-to-Treat Population

The modified Intention to Treat (mITT) population includes all randomized subjects that received at least one dose of study medication. For change from baseline analyses, this includes only those subjects that had a baseline assessment and at least one post-baseline efficacy assessment. This analysis population will be used for the primary and secondary efficacy analyses.

4.1.4 Per Protocol Population

The per-protocol (PP) population includes all mITT subjects with no relevant protocol deviations through Week 48 as described in Section 2.4.

In addition, subjects with baseline NSAA total score of less than 15 points will be excluded from the per-protocol population, based on the August 2018 protocol amendment which added a screening NSAA assessment and an exclusion criterion for those subjects with a screening NSAA score of less than 15.

4.1.5 Safety Population

The Treated Subjects / Safety Population includes all enrolled subjects who received at least one dose of study therapy.

If a subject received the same incorrect treatment throughout the study, then the subject will be analyzed based on the treatment received.

If a subject received study drug from more than one treatment group, then the subject will be analyzed based on the first treatment received.

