### Study Treatment:

Each participant will be administered weekly, SC doses of RO7239361 (previously, BMS-986089) or placebo for 48 weeks in a randomized, double-blind design. Participants who complete the 48-week double-blind phase are eligible to receive OL RO7239361 (active treatment) as part of an OL extension phase of this study. The OL extension phase will last up to 192 weeks or until RO7239361 is commercially available in the subject's country, per local regulations, or the study is terminated by the Sponsor, whichever comes first. Please refer to [Section 7.8](#) for details regarding treatment after the end of study. Doses in the OL extension phase may be adjusted based on emerging data.

| Study Drug                 |                            |           |
|----------------------------|----------------------------|-----------|
| Medication                 | Potency                    | IP/Non-IP |
| RO7239361 7.5 mg dose      | 10.7 mg/mL (0.7mL/syringe) | IP        |
| RO7239361 15 mg dose       | 21.4 mg/mL (0.7mL/syringe) | IP        |
| RO7239361 35 mg dose       | 50 mg/mL (0.7mL/syringe)   | IP        |
| RO7239361 50 mg dose       | 71.4 mg/mL (0.7mL/syringe) | IP        |
| RO7239361 matching placebo | 0 mg/mL (0.7mL/syringe)    | IP        |

Other medications used as support medication for preventative, diagnostic, or therapeutic reasons, as components of the standard of care for a given diagnosis, may be considered as non-investigational products. In this study, corticosteroids are considered *a* non-investigational product and will not be provided by the sponsor.

Study drug preparation and administration instructions will be provided in a separate manual.

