**Table 7-1: Study Treatments**

| Product Description /Class and Dosage Form | Potency | IP/Non-IMP | Blinded or Open Label  | Packaging / Appearance   | Storage Conditions (per label)                        |
|---|----------------|-------------------|---|---|--|
| RO7239361 injection
7.5 mg/syringe             | 10.7 mg/mL     | IP                | Blinded (during the 48-week double-blind phase ) and Open Label (during the 192-week OL phase ) | Solution packaged in a 1 cc glass syringe equipped with a safety syringe device
Secondary packaging is either a 1 syringe carton or 4 syringe carton | 2-8° C (36-46° F), protect from light, protect from freezing |
| RO7239361 injection
15 mg/syringe              | 21.4 mg/mL     | IP                | Blinded (during the 48-week double-blind phase ) and Open Label (during the 192-week OL phase ) | Solution packaged in a 1 cc glass syringe equipped with a safety syringe device
Secondary packaging is either a 1 syringe carton or 4 syringe carton | 2-8° C (36-46° F), protect from light, protect from freezing |
| RO7239361 injection
35 mg/syringe              | 50 mg/mL       | IP                | Blinded (during the 48-week double-blind phase ) and Open Label (during the 192-week OL phase ) | Solution packaged in a 1 cc glass syringe equipped with a safety syringe device
Secondary packaging is either a 1 syringe carton or 4 syringe carton | 2-8° C (36-46° F), protect from light, protect from freezing |
| RO7239361 injection
50 mg/syringe              | 71.4 mg/mL     | IP                | Blinded (during the 48-week double-blind phase ) and Open Label (during the 192-week OL phase ) | Solution packaged in a 1 cc glass syringe equipped with a safety syringe device
Secondary packaging is either a 1 syringe carton or 4 syringe carton | 2-8° C (36-46° F), protect from light, protect from freezing |
| Placebo for RO7239361 injection                   | 0 mg/mL        | IP                | Blinded   | Solution packaged in a 1 cc glass syringe equipped with a safety syringe device
Secondary packaging is either a 1 syringe carton or 4 syringe carton | 2-8° C (36-46° F), protect from light, protect from freezing |

Oral CS will be obtained by standard prescribing procedures.

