### **10.2 Populations for Analyses**

For purposes of analysis, the following populations are defined:

| Population                  | Description  |
|------------------------------------|---|
| Enrolled                           | All participants who sign informed consent and are assigned a participant identification number.  |
| Randomized                         | Enrolled participants who receive a randomization treatment assignment.   |
| Treated                            | 
Enrolled subjects who receive at least 1 dose of study therapy.
 
 
• If a subject received the same incorrect treatment throughout the study, then the participant will be analyzed based on the treatment received.
 
• If a subject received study drug from more than one treatment group, and none of the administrations were consistent with the assigned randomized treatment group, then the participant will be analyzed based on the first treatment received.
 
 |
| Modified Intention to Treat (mITT) | Randomized subjects that received at least one dose of study drug . For change from baseline analyses, this includes only those subjects that had at least one efficacy assessment.  |
| Per-Protocol                       | mITT subjects with no major protocol violations, as described in the Statistical Analysis Plan   |

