2.3 DETERMINATION OF SAMPLE SIZE

The sample size of 159 subjects (53 subjects per arm) will provide 80% power for testing the null hypothesis of no difference between a dose of RO7239361 and placebo, and 90% power for testing the null hypothesis of no difference between the pooled doses of RO7239361 and placebo, at a 2-sided α -level of 0.05 in the change from baseline in NSAA total score at 48 weeks, under the following assumptions:

- A true treatment difference (RO7239361 minus placebo) of 2.5 points
- A standard deviation of 4.4 points
- A treatment discontinuation rate of 5%.

For this study design and analysis, the minimum detectable difference is approximately 1.53 points for the comparison of the pooled dose groups to placebo, and 1.75 points for the comparison of an individual dose group to placebo.

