4.7 SAFETY ANALYSES

Adverse events, including abnormal laboratory findings, will be defined using the National Cancer Institute (NCI) Common Terminology for Adverse Events (CTCAE, version 5), and will be coded according to the most recent Medical Dictionary for Regulatory Activities (MedDRA) version. Adverse events will be summarized according to the MedDRA coded Preferred Terms (PT) by System Organ Class (SOC). Previous and concomitant medications will be coded using the WHO Drug Dictionary version.

The evaluation of safety is based on clinical AEs, vital signs, echocardiogram, ECG results, and clinical laboratory results reported during the study. Cardiac MRI measures

may also be included in the safety assessment. Safety analyses will be performed using the treated subjects. For AEs, all enrolled subjects will be listed.

Safety analysis data displays will be generated for the following:

- the double-blind treatment period, with baseline defined as the last visit prior to the start of the double-blind treatment period
- all active treatment during both the double-blind and open-label treatment periods (excluding data from the placebo subjects during the double-blind period); for this analysis, baseline will be defined as the last visit prior to the start of active treatment for each subject (i.e., the start of double-blind treatment period for those subjects randomized to active treatment from study start, or the start of the open-label treatment period for those subjects randomized to double-blind placebo and who are switching to active treatment at the start of the OLE).

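### SAP 4.1.5 drops a protocol condition, so one wrong first dose followed by correct dosing moves a boy's double-blind safety data to the wrong arm

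*SAP*

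**What the plan says.** SAP 4.1.5 (Safety Population) has two rules for boys who were not treated as randomised. The first covers a constant error: "If a subject received the same incorrect treatment throughout the study, then the subject will be analyzed based on the treatment received". The second covers mixed treatment: "If a subject received study drug from more than one treatment group, then the subject will be analyzed based on the first treatment received". It carries no further condition.

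Protocol 10.2, in its definition of the treated population, has the same first rule. Its second rule has an added condition: "and none of the administrations were consistent with the assigned randomized treatment group". The copy of the protocol attached to the SAP as Appendix 1 contains that condition too. The SAP body gives no reason for leaving it out and does not present it as a change.

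SAP 4.7 makes this the population for safety: "Safety analyses will be performed using the treated subjects".

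**The concern.** The SAP body and the protocol give different instructions for the same boys. Under the SAP, a single administration, the first, fixes the arm for everything that follows. A boy randomised to high dose who is given a placebo syringe on Day 1 and correct syringes afterwards is tabulated as a placebo boy. Any event he has on active drug then counts against placebo. In the reverse case, a placebo boy's events count against active drug. If the first error is between the two active doses, events move between those arms only.

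The arms are small, and the protocol lists serious adverse events and adverse events leading to discontinuation among its secondary endpoints, tabulated by arm. One displaced event can therefore be seen in the tables.

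**Working it through.** **Inputs**
- Dosing: weekly study drug "or placebo for 48 weeks in a randomized, double-blind design" (Protocol synopsis, Study Treatment). I take this as 48 doses. It would be 49 if a double-blind dose is also given at the Week 48 visit.
- Carton size: "Secondary packaging is either a 1 syringe carton or 4 syringe carton" (Protocol Table 7-1).
- Arm size: "The sample size of 159 subjects (53 subjects per arm) will provide 80% power" (SAP 2.3).

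**Arm size, used here only as a denominator.** With a difference of 2.5, SD 4.4, two-sided 0.05 and 80% power, n = 2 × (1.960 + 0.842)² × 4.4² / 2.5² = 48.6, so 49 per arm. Allowing for 5% discontinuation, 49 / 0.95 = 51.6, so 52 per arm and 156 in total, against the stated 159. With 53 × 0.95 = 50.35 evaluable per arm, power is 81.4%. The stated 53 per arm is consistent with its assumptions.

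**The two rules applied to 48 doses.** P is placebo, L low dose, H high dose. Where some doses match the randomised arm, the protocol column uses as randomised, which the protocol implies but does not write.

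| Randomised | Doses received | Share correct | SAP arm | Protocol arm |
|---|---|---|---|---|
| P | 1 H, then 47 P | 47/48 = 97.9% | H | P |
| P | 4 H (one wrong carton), then 44 P | 44/48 = 91.7% | H | P |
| H | 1 P, then 47 H | 47/48 = 97.9% | P | H |
| P | 20 P, 4 H, 24 P | 44/48 = 91.7% | P | P |
| P | 1 P, then 47 H | 1/48 = 2.1% | P | P |
| P | 48 H | 0% | H | H |
| P | 10 L, then 38 H | 0% | L | L |
| P | 47 H, then 1 P | 1/48 = 2.1% | H | P |

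The rules disagree only when the first dose is wrong and at least one later dose is right (rows 1, 2, 3 and 8). In rows 1 to 3 the SAP puts a mostly correctly treated boy in the wrong arm. In row 8 the SAP arm matches his exposure and the protocol arm does not. In row 5 both rules misplace him.

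**Size per boy.** One dose of 48 (2.1%; 1/49 = 2.0% with 49 doses) decides the arm for all of his double-blind safety data. He is 1/53 = 1.9% of an arm, and the two denominators become 52 and 54.

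**Illustration with assumed counts.** Suppose placebo and high dose each have 3/53 boys with a given event (5.7%), and one placebo boy with the event is moved to high dose. The table then reads 2/52 = 3.8% against 4/54 = 7.4%, an apparent gap of 3.6 percentage points where there was none.

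**The case against.** **Neither rule follows majority exposure.** Row 8 shows the protocol's rule making the same kind of error as the SAP's. This stands, and it is why the fix needs a listing. Still, an isolated early kit error that is then corrected is the more plausible pattern. Kits are obtained through the IWRS at each early visit, so a wrong Day 1 kit need not be repeated on Day 8.

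**The protocol does not say where a boy with some correct doses goes.** This stands. Copying the protocol sentence back would remove the wrong instruction but leave that case to inference, so the default has to be written out.

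**The error may never happen.** The first three doses are given at the site, and no document reports a wrong kit or an error rate. The 1.9% is the weight of one hypothetical boy, not an expected effect.

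**Other outputs would reveal it.** SAP 4.7.1 plans listings of drug administration, randomisation schedule and batch numbers, and serious events are listed by boy. A mismatch could be traced, but the summary tables would still be wrong. The incorrect-treatment deviation in SAP Section 3 does not help: it governs the per-protocol set, and a single wrong dose is below its threshold.

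**The SAP may refine the protocol.** Protocol 10.3 does leave the selection of participants to the SAP. That would allow a stated and justified change, and this one is neither.

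**Conclusion.** The SAP is wrong as written, at low severity. It conflicts with the protocol without explanation, and following it gives the wrong arm for a boy with one wrong first dose and correct dosing afterwards.

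The size is one boy at a time: all of his double-blind safety data, or 1.9% of a 53-boy arm. This assumes about 48 doses and the planned arm size. The frequency is unknown and probably very low.

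A reader might infer three stronger conclusions, and the documents support none of them:
- That any dispensing error distorts the safety comparison. The two rules agree when the wrong kit comes later, when only the first dose is right, when the same wrong treatment is given throughout, and when no dose is right.
- That the efficacy result is at risk. Primary and secondary efficacy use the mITT population (SAP 4.1.3), which has no as-treated rule. The planned safety outputs are descriptive, with no formal safety test specified.
- That the protocol's rule is always the more accurate one. It is not when the exposure is mostly incorrect.

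**What to change.** Amend the second rule in SAP 4.1.5 as follows:

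1. Limit it to the double-blind period. Read literally, the present wording also covers every placebo boy who moves to active drug in the open-label phase, a switch that SAP 4.7 handles through separate displays.
2. Restore the protocol's condition: "and none of the administrations were consistent with the assigned randomized treatment group".
3. State explicitly that a boy with at least one dose of his assigned treatment is analysed as randomised.
4. List every mixed-treatment boy with his randomised arm and the dates and number of incorrect doses, so that a boy with mostly incorrect exposure is visible.

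If the sponsor meant to change the protocol's rule, the SAP should say so and give the reason. The cost is one clause and one short listing, settled before unblinding. No data collection or efficacy analysis changes.

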4.2 ANALYSIS OF STUDY CONDUCT

Summary tables will be provided for pre-randomization subject status, end of double-blind phase subject status, and end of open-label phase subject status. Summary tables will reflect information about the number and proportion of subjects who are enrolled, randomized, and who have completed the double-blind and open-label extension periods. Reasons for not being randomized and not completing the treatment periods will also be summarized.

4.3 ANALYSIS OF TREATMENT GROUP COMPARABILITY

Demographic characteristics such as gender, age, race, and ethnicity will be summarized for all treated subjects. Summary tables will be provided for the dosage and duration of prior use of CS (e.g., prednisone, prednisolone, or deflazacort). Summary tables will also be provided for baseline values of the NSAA total score, timed function tests, and pulmonary function tests.

4.4 EFFICACY ANALYSIS AT END OF DOUBLE-BLIND TREATMENT

4.4.1 Primary Efficacy Endpoint

The primary analysis, on the change from baseline in NSAA total score after 48 weeks of double-blind treatment, will be conducted using a Mixed Model Repeated Measures (MMRM) analysis with treatment, visit, treatment-by-visit interaction, age stratum, and CS stratum entered into the model as fixed effects, and subject entered as a random effect. The baseline value of the NSAA total score will be entered into the model as a covariate. The modified ITT population will be the analysis population for the primary

efficacy analysis. An unstructured correlation within subject will be used. In the case that this does not converge, a compound symmetry structure will be used.

For each RO7239361 dose group, the null hypothesis of no treatment difference between the dose group and placebo will be tested using the estimates from this MMRM model at the end of the 48-week double-blind treatment period. In order to control the overall Type I error rate for the analysis of the primary endpoint, the following testing procedure (based on the closed testing principle) will be implemented:

1. Comparison of the pooled RO7239361 doses to placebo (intersection hypothesis) at a 2-sided α -level of 0.05 is performed.
2. If the result from the previous step is significant, then a comparison of the RO7239361 high dose (35/50 mg) to placebo and a comparison of the low dose (7.5/15 mg) to placebo will both be performed at a 2-sided α -level of 0.05.

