### **Number of Participants:**

Statistical Considerations:

Sample Size:

[figure not shown]
Assuming the standard deviation of the NSAA is 4.4 points, with approximately 150 evaluable subjects, the final analysis will have 80% power to detect a between group difference of 2.5 points. The number randomized will be increased to allow for an approximate dropout rate on the order of 5% at the primary analysis, so approximately 159 participants will be randomized. Approximately 15 of these participants will be randomized in Japan, and the remaining participants will be randomized outside of Japan.

The final analysis will test for differences between each RO7239361 treatment and placebo in either direction. The doses will be tested against placebo in a hierarchical manner, with the high dose (Dose 2) tested versus placebo in the first step of the hierarchy. If the null hypothesis of no difference between the high dose and placebo is rejected in favor of the RO7239361 dose at a two-sided  $\alpha$  level of 0.05, then the low dose (Dose 1) will be tested against placebo.

The primary analysis, on the change from baseline in NSAA total score, will be conducted using a mixed model repeated measures (MMRM) analysis with treatment, visit, and the treatment-by-visit interaction entered into the model as fixed effects, and participant entered as a random effect. The baseline value of the NSAA total score will be entered into the model as a covariate. The stratification factors will be entered into the model as blocks.

Sensitivity analyses will include the following: an analysis of covariance (ANCOVA) using the modified intent-to-treat (mITT) data set; an ANCOVA on the mITT data set with missing data imputed using multiple imputations; and an MMRM analysis using the per-protocol data.

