## **5 STUDY DESIGN**

### **5.1 Overall Design**

This is a multi-center, randomized, double-blind, placebo-controlled study to assess the efficacy, safety and tolerability of two different weekly SC doses of RO7239361 in ambulatory boys with Duchenne muscular dystrophy (DMD).

Eligible participants will be randomized to receive doses of RO7239361 or placebo (1:1:1 across the three treatment arms). The randomization will be stratified by:

- Age (6 through 7 and 8 through 11)
- CS regimen: daily (prednisone, prednisolone or deflazacort) vs intermittent (any non-daily dosing of prednisone, prednisolone or deflazacort)

A separate randomization will be conducted for Japan (N~15) with stratification for age only (6 through 7 and 8 through 11), not CS regimen.

[figure not shown]
RO7239361 or placebo will be administered weekly. The first three doses (Days 1, 8 and 15) of study *drug* must be administered at the site. Parents/caregivers will be trained to administer SC injections during the first three dose administrations. Parents/caregivers who are comfortable with SC administration can administer the injection at home starting at Day 22. Parents/caregivers will be dispensed an approximately 6 week supply of drug in pre-filled syringes (RO7239361 or matching placebo) for weekly study drug/placebo administration to the participant.

After completion of this 48-week double-blind phase, participants may enter the *OL* phase in which all participants will receive active RO7239361 study drug. Participants originally randomized to active drug will continue to receive the dose to which they were originally randomized. Participants originally randomized to placebo will be randomized to the high or low dose of RO7239361 on Day 1 of the *OL* phase. Dose assignment in the *OL* phase may be modified based upon emerging safety findings. Subjects entering the *OL* phase will remain blinded to their original dose assignment. *Participants* who discontinue study *treatment* at any *timepoint* (i.e., *early discontinuation for patients* who do not enter the *OL* phase or *at termination of the OL phase*) will enter the follow-up phase of the study. The follow-up phase of the study is 24 weeks. Participants will be monitored for safety at three visits in the follow-up phase. Participants should provide immunogenicity samples at all follow-up visits.

The study design schematic is presented in [Figure 5.1-1](#).

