### 10.3.1 Efficacy Analyses

| Endpoint    | Statistical Analysis Methods  |
|-------------|---|
| Primary     | 
The primary analysis, on the change from baseline in NSAA total score, will be conducted using a Mixed Model Repeated Measures (MMRM) analysis with treatment, visit, and the treatment-by-visit interaction entered into the model as fixed effects, and participant entered as a random effect. The baseline NSAA total score will be entered into the model as a covariate. The stratification factors will be entered into the model as blocks.
 
For each RO7239361 dose group, the null hypothesis of the no treatment difference between the dose group and placebo will be tested using the estimates from this MMRM model at the end of the 48-week double-blind treatment period. In order to control the overall type I error rate for the analysis, the following hierarchical testing of doses will be implemented:
 
 
1. Comparison of the RO7239361 high dose (35/50 mg) to placebo at a two-sided <math>\alpha</math> level of 0.05 is performed.
 
2. If the null hypothesis for the high dose is rejected (comparison of the high dose to placebo in the previous step is statistically significant), then a comparison of the RO7239361 low dose (7.5/15 mg) to placebo at a two-sided <math>\alpha</math> level of 0.05 will be performed. If the null hypothesis for the high dose is not rejected, then the testing of the low dose versus placebo will not be performed.
 
 
Sensitivity analyses will include the following: an analysis of covariance (ANCOVA) using the mITT data set; an ANCOVA on the mITT data set with missing data imputed using multiple imputations; and an MMRM analysis using the per-protocol data.
 |

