2. STUDY DESIGN

This is a multi-center, randomized, double-blind, placebo-controlled study to assess the efficacy, safety, and tolerability of two different weekly subcutaneous (SC) doses of RO7239361 in ambulatory boys with Duchenne muscular dystrophy (DMD).

Eligible subjects will be randomized to receive doses of RO7239361 or placebo (1:1:1 across the three treatment arms). The randomization will be stratified by:

- Age (6 through 7 and 8 through 11)
- Corticosteroid (CS) Regimen: daily (prednisone, prednisolone, or deflazacort) vs intermittent (any non-daily dosing of prednisone, prednisolone, or deflazacort).

[figure not shown]
A separate randomization will be conducted for Japan (N=17) with stratification for age only (6 through 7 and 8 through 11), not CS regimen.

RO7239361 or placebo will be administered weekly. The first three doses (Days 1, 8, and 15) of study medication must be administered at the site. Parents/caregivers will be trained to administer SC injections during the first three dose administrations.

Parents/caregivers who are comfortable with SC administration can administer the injection at home starting at Day 22. Parents/caregivers will be dispensed an approximately 6 week supply of drug in pre-filled syringes (RO7239361 or matching placebo) for weekly study drug/placebo administration to the subject.

After completion of this 48-week double-blind phase, subjects may enter the open-label phase in which all subjects will receive active RO7239361 study drug. Subjects originally randomized to active drug will continue to receive the dose to which they were originally

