4.4.2 Secondary Efficacy Endpoints

The secondary efficacy analyses will compare the change from baseline to week 48 between each RO7239361 dose group and the placebo group, for the following endpoints.

- 4SCV
- 6MWD
- 95% stride velocity (SV95C)
- Stand from supine velocity
- 10-meter walk/run velocity
- PODCI transfers and basic mobility subscale
- Proximal lower extremity flexor (knee extension and knee flexion) strength measured using manual myometry
- CGI-C

MMRM models similar in structure to that used for the primary analysis will be used for the continuous secondary efficacy endpoints, with the exception of proximal lower extremity flexor strength (which will be tested using a multivariate analysis of variance of the 2 component variables: knee extension and knee flexion).

The distribution of CGI-C and CaCGI-C responses at week 48 will be summarized using descriptive statistics. Categorical analysis of the number of subjects falling into pre-specified categories (i.e., 'any improvement or no change' vs. 'any worsening') will be performed using a Cochran-Mantel-Haenszel test using age category and CS use as stratification factors.

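### Japan is randomised from its own list, stratified by age only, but no efficacy analysis has a term for that list; adding one is a free improvement of minor size

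*SAP*

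**What the plan says.** Both documents describe two randomisations. SAP section 2 states: "A separate randomization will be conducted for Japan (N=17) with stratification for age only (6 through 7 and 8 through 11), not CS regimen". Protocol 5.1 has the same arrangement with an approximate number: "A separate randomization will be conducted for Japan (N~15) with stratification for age only". The protocol synopsis counts these boys within the 159: "Approximately 15 of these participants will be randomized in Japan, and the remaining participants will be randomized outside of Japan". Nothing removes them from the modified ITT population used for the primary analysis.

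For the primary model, Protocol 10.3.1 says: "The stratification factors will be entered into the model as blocks". The factors that both documents list by name are age group and CS regimen. SAP 4.4.1 accordingly has "treatment-by-visit interaction, age stratum, and CS stratum entered into the model as fixed effects", with baseline NSAA as covariate. The ANCOVA in SAP 4.4.4 uses the same two strata. For CGI-C, SAP 4.4.2 plans a "Cochran-Mantel-Haenszel test using age category and CS use as stratification factors".

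No efficacy analysis contains a Japan, region or list term. SAP 3.1 describes randomisation by age and CS regimen for all eligible boys and does not mention the Japanese list.

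**The concern.** A separate list acts as a stratum whether or not it is called one: arms are balanced within Japan and, separately, within the rest of the world. The usual rule is to adjust for whatever restricted the allocation. When such a factor is prognostic and is left out, restriction has already removed between-list variation from the treatment contrast, but the model still counts that variation as error. The reported standard error is then larger than the true variability of the estimate, and some power is lost.

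There is also an operational gap. The primary model needs a CS stratum for every boy, and Japanese boys were never assigned one at randomisation. The SAP should say where the value comes from. The CMH strata matter as well, because CGI-C is fifth in the SAP's type I error-controlled hierarchy.

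**Working it through.** **1. The plan's own sample size.** Inputs from SAP 2.3: difference 2.5, SD 4.4, two-sided 0.05, power 80%, 5% discontinuation.
- n per arm = 2 × (1.960 + 0.842)² × 4.4² / 2.5² = 48.6, so 49.
- Total 147; 147/0.95 = 154.7, so 155, within 3% of 159.
- With the protocol's 150 evaluable (50 per arm), 50/0.95 = 52.6, so 53 per arm and 159 in all. Power at 50 per arm is 81.1% (normal) or 80.3% (t).

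The stated figure reproduces. A list term does not change the planned N.

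**2. Cells randomised against cells analysed.** Outside Japan there are 2 ages × 2 CS regimens = 4 cells. Japan has 2 age cells. That makes 6 randomised cells; the analyses recognise only the 4 age-by-CS combinations. Japan's share is 15/159 = 9.4% or 17/159 = 10.7%.

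**3. Excess in the standard error.** Let p = 17/159 and let D be the difference in mean Week 48 change between Japan and elsewhere that remains after baseline NSAA, age and CS. The documents give no value, so D is an assumption.
- Omitted variance = p(1 − p)D² = 0.0955 D².
- Share of 4.4² = 19.36: 0.5%, 2.0% and 4.4% for D = 1, 2 and 3.
- Excess in SE = 1 − √(1 − share): 0.2%, 1.0% and 2.2%.

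**4. Chance imbalance.** Seventeen boys cannot divide equally among three arms. With blocks of three in two age strata (block size is not stated), the worst split is 7, 5, 5. Two extra boys in an arm of 53 shift the contrast by (2/53) × D = 0.04 to 0.11 points for D = 1 to 3.

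**5. Simulation.** A Week 48 linear model was fitted with and without a Japan term, 2,000 runs per scenario. Assumptions: 151 evaluable boys, 15 or 17 in Japan, residual SD 4.4, blocks of three within each cell, even age split with a 2-point effect, CS effect 1.5 points, intermittent CS in 30% outside Japan and 0% or 80% in Japan. Baseline NSAA and repeated visits were not modelled. Each entry is the range over four scenarios, without the term then with it.

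| Japan shift (points) | Type I error | Power at 2.5 points | Mean SE (power runs) |
|---|---|---|---|
| 0 | 4.6–5.3%; 4.7–5.2% | 81.2–82.7%; 81.0–82.9% | 0.874–0.879; 0.875–0.879 |
| 2 | 4.3–5.3%; 4.2–5.4% | 78.5–81.2%; 79.1–81.7% | 0.881–0.884; 0.874–0.877 |
| 4 | 3.5–4.6%; 4.3–5.4% | 78.1–78.9%; 80.5–81.2% | 0.906–0.912; 0.877–0.878 |

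Monte Carlo error is about √(0.05 × 0.95/2000) = 0.5 points for type I error and √(0.8 × 0.2/2000) = 0.9 points for power. Mean estimates with and without the term agree to within 0.002 points throughout. The spread of the estimates is also almost the same either way: at a 4-point shift with 17 boys and no intermittent CS in Japan, the null-run SD is 0.88 for both models. Only the model-based SE changes, so the error is conservative.

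**6. CMH cell sizes.** One dose against placebo uses about two thirds of the Japanese boys: 17 × 2/3 ≈ 11, spread over two age cells.

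**The case against.** The strongest objection is that the SAP follows its protocol. Protocol 10.3.1 calls for the stratification factors, the documents name age and CS regimen, and SAP 4.4.1 enters both. A reader might infer that the SAP breaches the protocol rule, but the text does not support that. That a separate list works as a stratum is a statistical argument, not a contradiction between passages. This part of the objection stands.

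A reader might also infer that the treatment estimate is biased or the type I error inflated. Neither follows: allocation is randomised 1:1:1 in both lists, the estimates do not move, and the error is conservative.

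Nor is it wrong to adjust Japanese boys for CS regimen. It is a baseline characteristic, with a full CS history taken at screening (Protocol Table 2-1) and a baseline regimen defined in SAP 4.7.1.3, and adjustment is valid without stratification. One might suppose that Japanese boys would drop out of the model because their CS stratum is missing in the randomisation system. That depends on programming the documents do not describe, so it is a gap to close and not a predicted loss.

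The size argument also has force. D is undocumented, and trained evaluators, video review and the stable-CS criterion all work to limit regional differences. The 2-point power gain needs an assumed 4-point shift, larger than the design effect. SAP section 2 does describe both lists, so the silence in SAP 3.1 is a wording gap. Finally, the CMH remedy drops CS within Japan and leaves sparse cells there.

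What remains is that the groups used for allocation are not all represented in the analysis, that representing them is nearly free, and that the source of CS stratum for Japan is unstated.

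**Conclusion.** The point holds as a minor refinement. Japan is randomised separately and by age only, and no efficacy analysis reflects this. The consequence is a standard error about 0.2% to 2.2% too large if Japan differs by an assumed 1 to 3 points after the other covariates, with no bias in expectation. If Japan does not differ, nothing changes beyond simulation error. At an assumed 4-point shift, adding the term gains about 2 points of power. No conclusion of the trial would be invalid without it. The textual finding is firm; its size rests on the assumed regional difference, CS mix and block size.

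**What to change.** - **MMRMs and ANCOVA (SAP 4.4.1, 4.4.2, 4.4.4):** add randomisation list (Japan versus rest of world) as a fixed effect in the primary and secondary MMRMs and in the ANCOVA. Keep CS regimen as a covariate for all boys.
- **CS stratum:** state that CS regimen for Japanese boys is taken from baseline CRF data.
- **CGI-C CMH test (SAP 4.4.2):** stratify by the six cells randomised, that is Japan by age and rest of world by age and CS. Say that CS is not used within Japan because it was not used there in allocation, and accept that the Japanese cells are sparse.
- **SAP 3.1:** describe both randomisations, consistent with SAP section 2.

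The cost is SAP wording, one degree of freedom in each MMRM and ANCOVA, and two more CMH strata. Sample size, conduct and data collection are unaffected. The change should be made before unblinding so that it is not read as post hoc.
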